4.1.2 Allocation concealment mechanism

- 1) In this study, the surgical procedures will be selected in a randomized manner, and the CTU members will place the intervention modality in an envelope and give it to each center's coordinator who is not involved in the implementation of the intervention or the observation of the outcome to manage the allocation. The envelope will be opened by the investigators at each center following the enrollment order, to realize blinded preoperative randomization.
- 2) Data will be entered by dedicated study staff, who will be blinded to the randomization allocation and surgical procedure.

4.1.3 Assignment implementation (who generates the serial numbers, who recruits the subjects, and who assigns them)

- 1) The surgeons will perform the recruitment and obtain informed consent, and perform the surgical procedure.
- 2) The CTU team designs the randomization method and generates the corresponding

envelopes.

- 3) The allocation of surgeries according to the order of informed consent signed by the study participants in each center according to the randomization method to achieve an equal distribution of reporters in the open and lumpectomy groups.
- 4) The randomization staff will record the randomization numbers and procedure.
- 5) Follow-up of each patient and recording of relevant data and adverse events will be performed by dedicated follow-up personnel.
- 6) Data entry into the RedCap database will be performed by dedicated data entry personnel.
- 7) The CTU and the principal investigator will perform statistical analyses.

4.2 Blinding

4.2.1 Who to blind and how to implement it

- 1) The specific procedure will not be known to the surgical team of each center until after the patients have been randomized during the administration phase of the intervention.
- 2) The randomization process will not be known to data entry personnel after the operation.
- 3) Statisticians will also be unaware of the randomization process.
- 4) The randomization process is also unknown to the personnel responsible for endpoint evaluation.

4.2.2 Unblinding

- 1) The total randomization form will be kept exclusively by the dedicated staff at each center, and a letter which contains information of the group assignment and the surgical method will be set up for each group with the number.
- 2) The unblinding will be conducted to reveal the information of each patient with corresponding surgical procedure, only after final data analyses.
- 3) Since this study does not involve drug use, there is no emergency unblinding process in place.

V. Methods of data collection, management and analysis

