4.1 Allocation of the interventions

4.1.1 Allocation sequence generation: In this study, a centralized block randomization with a block size of 6 will be used to randomly assign patients to the laparoscopic surgery group or the open surgery group at a 1:1 ratio. The randomization scheme will be completed by an independent statistical team at the Clinical Trial Center of the Children's Hospital of Fudan University by creating and sequencing random seed numbers (SAS 9.4 software). The intervention protocols determined by the random assignment sequence will be in sequentially numbered, non-transparent, sealed envelopes by zone: each of the 6 subgroups for each zone will be placed sequentially in six small, non-transparent, sealed envelopes numbered from 1 to 6, and then uniformly placed in the same large envelope marked with the corresponding zone number. The randomization assignment will be administered by the central coordinator at the Obstetrics and Gynecology Hospital of Fudan University who is not involved in the implementation of the intervention or the outcome observation. The enrollment is competitive, and the sub-center coordinator will contact the central coordinator before the inclusion of the first patient in each group. The central coordinator will follow the randomization scheme and assign the large envelopes with the group numbers to each center following the order of contact. Each sub-center will open the envelopes according to the order of signing the informed consent form, and strictly follow the numbered order of the envelopes, and then inform the participating physicians of the assignment scheme and complete written registration form.

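### Section 4.2.2 places the total randomisation form with staff at each centre, which on its plain wording conflicts with the centralised allocation in 4.1.1 and leaves concealment open

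*Combined protocol and SAP*

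**What the plan says.** Three sections describe who handles the allocation.

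- **4.1.1 (sequence generation).** The design is described as "a centralized block randomization with a block size of 6 will be used to randomly assign patients". On who generates it: "The randomization scheme will be completed by an independent statistical team at the Clinical Trial Center of the Children's Hospital of Fudan University". On who runs it: "The randomization assignment will be administered by the central coordinator at the Obstetrics and Gynecology Hospital of Fudan University". Each block of six sealed, numbered envelopes goes into a large envelope bearing its zone number. Enrolment is competitive, and the coordinator is to "assign the large envelopes with the group numbers to each center following the order of contact". After opening an envelope, the sub-centre completes a written registration form.
- **4.1.2 and 4.1.3 (concealment and implementation).** Trial-unit members hand envelopes to each centre's coordinator, who is to have no part in treatment or outcome observation. Then: "The envelope will be opened by the investigators at each center following the enrollment order". Item 1 of 4.1.3 adds: "The surgeons will perform the recruitment and obtain informed consent, and perform the surgical procedure". Item 4 has randomisation staff record the numbers.
- **4.2.1 and 4.2.2 (blinding and unblinding).** The surgical team is not to know the procedure until the patient has been randomised. Section 4.2.2 1) then says: "The total randomization form will be kept exclusively by the dedicated staff at each center". It adds that numbered letters giving group and surgical method will be set up, without naming a holder. Item 2 reserves unblinding until after the final analyses, and item 3 says there is no emergency unblinding.

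**The concern.** The surgeon knows the arm once the envelope is open, so concealment up to that moment is the main protection against selective enrolment. The same surgeons recruit, take consent and operate, and investigators at the same centre open the envelopes. Under 3.13, eligibility is reviewed after consent and before randomisation. Some criteria in 2.2 involve judgement, such as fitness for surgery and expected cooperation with follow-up.

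If the next assignment can be looked up, a patient could be delayed, discouraged or judged ineligible according to the arm coming next. The groups would then differ in prognosis before treatment, and analysing patients as randomised would not correct that. In a non-inferiority trial with an 8-point margin on 5-year overall survival, such an imbalance could push the conclusion in either direction.

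**Working it through.** **The plan's own figures.** With 72% in both arms (equality is assumed; 3.12 states only the open-surgery rate), a margin of 8 points, one-sided alpha 0.025 and 80% power:

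- n per arm = (1.960 + 0.842)² × 2 × 0.72 × 0.28 / 0.08² = 7.849 × 0.4032 / 0.0064 = 494.5, rounded up to 495, as stated.
- 495 / 0.90 = 550 per arm, or 1100 in total; the next multiple of 6 is 1104, as stated, which is 1104 / 6 = 184 blocks.

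The custody question does not depend on these figures.

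**The custody statements side by side.**

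| Question | 4.1.1 | 4.1.2 and 4.1.3 | 4.2.2 1) |
|---|---|---|---|
| Who generates the scheme? | Independent statistical team | Trial unit | Not stated |
| Who administers allocation? | Central coordinator | Each centre's coordinator | Not stated |
| Who opens envelopes? | Sub-centre | Investigators at the centre | Not stated |
| Who holds the full list? | Not stated; central custody implied | Not stated | Dedicated staff at each centre, if the form is the list |

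1. Central, block-by-block release has little point if each centre already holds the whole scheme.
2. Sections 1 and 11.1 name six centres. A form kept exclusively at each of six places is hard to reconcile with itself.
3. A prospective list limited to one centre's own blocks could not exist in advance, because blocks go to centres in order of contact. A complete prospective form at a centre would therefore be the whole-trial list.
4. Large envelopes carry their zone number, so a holder of that list could match the block in hand and read its remaining assignments.

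**What the list adds to guessing within a block.** In a 1:1 block of size 2m, an assignment is certain once the other arm is used up. The expected number of certain assignments is 2m/(m + 1), so the share is 1/(m + 1). For m = 3 this is 1/4, or 0.25 × 1104 = 276 expected assignments. The share guessed correctly by always choosing the arm with more places left comes from exact enumeration.

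| Block size | Certain, no list | Guessed correctly, no list | Block in hand, with full list |
|---|---|---|---|
| 4 | 33.3% | 70.8% | 100% |
| 6 (plan) | 25.0% | 68.3% | 100% |
| 8 | 20.0% | 66.6% | 100% |
| 12 | 14.3% | 64.3% | 100% |

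The first two result columns assume the block size is known and earlier assignments in the block are tracked. The last column does not depend on block size, so larger or varying blocks would not cure the problem.

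**The case against.** The strongest reply is that the form is only a log. The protocol calls it a form, not a list or sequence, and never says it shows unopened assignments. Both 4.1.1 and 4.1.3 describe records of assignments already made. This reading is possible. However, the registration form in 4.1.1 is described separately, and 4.2.2 places the total form under unblinding beside letters prepared by number, which reads more like a key than a running log. The text settles neither reading.

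Other parts of the reply stand:

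- Section 4.1.1 never says who stores the list. Central custody is inferred from its description of a centralised scheme run by a central coordinator.
- Safeguards exist. The holders are dedicated staff, 4.1.2 keeps coordinators out of treatment and outcome observation, and 4.2.1 intends that surgeons do not know in advance. The gap is that the dedicated staff are not said to be separate from those who recruit.
- A reader might infer that the letters are also held at the sites. Section 4.2.2 names no holder.
- A reader might infer that the form serves no purpose, since there is no emergency unblinding. Section 4.2.2 2) does give one: revealing procedures after the final analyses. That purpose does not require the list to sit at a recruiting site during enrolment.

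**Conclusion.** The concern holds as a conflict of wording that, followed literally, weakens allocation concealment. If the form is the full list, all remaining assignments in the block a centre holds can be looked up, against 25% that are certain without it under the fixed block of 6. This rests on two assumptions: that the form covers unopened numbers, and that someone involved in recruitment could see it. The documents neither confirm nor exclude either.

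Three stronger readings go too far:

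- That a site could read off all its future assignments. Blocks are released competitively in order of contact, so only the block in hand can be matched reliably.
- That assignments have been disclosed. The documents show an exposure, not an event.
- That the bias can be sized from the survival figures by nodal status in 2.3 Prognosis. Those describe nodal status after lymph node dissection, which recruiters do not have before randomisation, and the share of patients steered would have to be invented.

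The size of any bias therefore cannot be derived from the documents. The wording should be corrected because concealment lost during enrolment cannot be restored at analysis.

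**What to change.** Replace 4.2.2 1) with wording to this effect: the full randomisation list is held only by the independent statistical team that generated it; the central coordinator releases sealed, numbered blocks; no recruiting centre, including the main centre, holds any document linking unopened numbers to arms; each site keeps only a log of opened envelopes (date, number, arm, patient ID), reconciled centrally with the list.

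Then align 4.1.1, 4.1.2 and 4.2.2 on who holds, hands over and opens the envelopes. State who holds the letters. Unblinding after the final analyses, as 4.2.2 2) intends, can be done from the independent team's copy. If only a log was meant, the same edit makes that clear.

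If any lists have already been distributed, retrieve them and record which centres held them and for how long.

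The cost is about one paragraph of protocol text plus any retrieval. The sample size stays at 1104, and no patients or staff are added.

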5.1 Data collection and patient retention

5.1.1 Protocols for estimating and collecting outcome indicators, baseline and other trial data

Based on the study protocol and data analysis plan, a case report form (CRF) has been developed and validated. Required fields are set to ensure the completeness of key data. The CRF will be completed by trained investigator at each site, and each enrolled case has to complete the CRF, which will be reviewed by the investigator and handed over to data manager for data entry and management at each site.

5.1.2 Improve patient engagement and completion of follow-up, including outcome data to be collected for patients who withdraw or change treatment methods

- 1) Detailed patient orientation by study team members at each center during the recruitment phase to achieve fully informed patients.
- 2) The study team members will provide long-term remote condition assessment services and related information consultation services for all study patients.
- 3) Patients will be followed up regularly by dedicated staff to reduce the rate of loss to follow-up.
- 4) The follow-up system will regularly remind the subjects of the follow-up time and the follow-up items according to the follow-up nodes.

5.2 Data management (entry, coding, encryption and storage)

5.2.1 Entry and coding protocols:

A database for data management and entry is designed based on the finalized CRF form. This study uses RedCap, which was developed by a professional CRO data management team, and the project data entry and management will be handled by dedicated personnel. To ensure the accuracy of the data, double entry should be performed by two research members independently, and blind verification and statistical analysis should be performed after software verification and manual error correction. The database will be locked after accuracy confirmation. The locked data files then will be submitted to an independent third-party statistical team for analysis. The statistical analysis plan (SAP) is developed by the statistical team during the study subject inclusion process, and finalized after repeated discussions with the investigator team, and uploaded to the clinical trial registry website before the last patient data collection is completed at the study registry website, or submitted for publication with the protocol.

5.2.2 Data storage and access

All information on research subjects is collected and stored in locked cabinets by dedicated personnel, and access to it is only possible with the relevant viewing privileges.

5.3 Statistical methods

5.3.1 Outcome statistical methods

Statistical analysis of the study will be undertaken by the CTU of the Children's Hospital of Fudan University. Interventions began at the study design stage, based on key scientific questions, clear design protocols, and statistical analysis methods based on the properties of the primary outcome indicators, whereby sample sizes were calculated based on expected effects. After study inclusion begins until the last patient data collection is completed, a detailed SAP is written and uploaded to the Clinical Trials Registry website. The following is an overview of the statistical analysis strategy and methods.

All analyses will be performed on an intention-to-treat (ITT) basis, except for sensitivity

analysis that will be performed according to per-protocol (PP) treatment.

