2.4 Laparoscopic surgery

Laparoscopic radical cervical cancer surgery was originally reported by Canis^[43] and Nezhat^[44] et al. In the last two decades, laparoscopic surgery has become increasingly sophisticated. In addition to traditional laparoscopic surgery, robotic-assisted surgery has been derived. Most studies have shown that laparoscopic surgery has less intraoperative bleeding and shorter hospital stay, and some studies have reported that the PFS rate of LRH was not inferior to that of ARH^[5-10]. Therefore, laparoscopic surgery has become the main treatment for early-stage cervical cancer in many countries, and the 2014 NCCN guidelines recommended a laparoscopic approach for radical cervical cancer. In most of the prestige hospitals in China, laparoscopic radical cervical cancer treatment accounts for more than 90% of the cases.

As previously mentioned, the LACC trial and the retrospective study published in the New England Journal of Medicine in late 2018 caused a huge impact in the medical community when they concluded that both PFS and OS rates for patients undergoing minimally invasive radical cervical cancer treatment were lower than those undergoing abdominal radical cervical cancer treatment. Following the publication of these articles, the version 3.2019 NCCN guidelines have recommended open surgery as the standard procedure for cervical cancer, and laparoscopic surgery is no longer recommended.

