3.1 Overall intervention plans

Minimally invasive radical cervical cancer treatment includes laparoscopic radical cervical cancer treatment (LRH) and robotic-assisted laparoscopic radical cervical cancer treatment, either of which can be chosen by the operator. This project focuses on the survival benefit of patients after minimally invasive and open radical cervical cancer

treatment, so radical cervical cancer treatment with preservation of reproductive function will not be included. For both open and minimally invasive radical cervical cancer surgery, the operation begins with a thorough abdominal exploration, including careful exploration of the diaphragm, and any metastatic lesions and metastatic sites should be described in detail in the operative record, with biopsy for confirmative diagnosis. If intra-abdominal lesions are found, radical cervical cancer surgery should not be used and should change to palliative treatment.

Pelvic lymph node dissection should be performed during radical cervical cancer surgery. Sentinel Lymph Node Mapping (SLN) is not included in this project, since there is no sufficient evidence for its sensitivity and specificity, and also the difficulty in achieving lymph node hyperstaging considering the large sample size of this project. If the tumor is ≥ 2 cm, or if the common iliac lymph node is positive for intraoperative freezing (optional), or if the preoperative evaluation of the paraaortic lymph nodes is positive, paraaortic lymph node dissection is preferred and followed by paraaortic lymph node biopsy. When clear the para-aortic lymph nodes, the upper border reaches the level of the inferior mesenteric artery is enough. The common iliac lymph nodes should be sent separately for examination, and the resection should include both sides of the common iliac vessels, with the upper border reaching the midpoint of the bifurcation of the abdominal aorta and the common iliac vessels and the lower border reaching the level of the bifurcation of the common iliac vessels.

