3.8 Criteria for Patient Withdrawal

Patients have the right to withdraw from the trial treatment or study at any time without any reason. The investigator also has the right to withdraw a patient from the trial treatment or study in the event of secondary disease, adverse events, protocol violations, administrative reasons, or other reasons. Participation in the study, whether or not the affected patient participates, will not affect the relationship between the patient and the physician and will not result in a loss of medical or other benefits to the patient. However, in such cases, the investigator will make appropriate efforts to determine and document the reasons for the patient's voluntary withdrawal from the study. If a patient withdraws from the study, a complete final evaluation should be conducted at the time of patient withdrawal. This will be reported along with the study results and all attempts to locate patients lost to follow-up will also be documented.

Patients will be seen by their physician if they withdraw from the study. According to routine gynecologic oncology protocols, they should continue to receive care and treatment from an experienced physician until further follow-up is deemed unnecessary

by the treating physician.

Patients will be withdrawn from the study under the following circumstances:

- 1) Study completion/termination, or death
- 2) Patient demands withdrawal
- 3) Patient is unable or unwilling to cooperate with follow-up
- 4) Patient has other serious, non-surgical complications
- 5) Patient's follow-up information cannot be obtained
- 6) The study is terminated or cancelled at the request of the sponsor
- 7) Other relevant reasons

If a patient moves to another treatment center and requires changing of physician, the investigator will make a reasonable attempt to locate that center's physician and request cooperation in order to complete the follow-up.

In many cases, patient withdrawal from the study constitutes discontinuation of treatment and/or discontinuation of completion of related forms, such as quality of life. In these cases, the investigator should obtain the patient's permission to continue monitoring their disease status (relapse, survival, toxicity, etc.) through the patient's record.

Excessive exit rates can make a study uninterpretable, and therefore, unnecessary subject dropouts should be avoided.

3.9 Combination and simultaneous treatment:

[figure not shown]

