5.3.2 Analysis of primary outcome data

a) This study is non-inferiority trial design, and the primary outcome is the rate of OS at 5 years. The hypothesis is as follows:

Hypothesis: Let π_1 denote the rate of OS at 5 years in the open surgery group, and let π_2 denote the rate of OS at 5 years in the minimally invasive surgery group, the non-inferiority margin =8%. The null hypothesis is $H_0: \pi_1 - \pi_2 \geq$ versus the alternative hypothesis is $H_1: \pi_1 - \pi_2 <$.

b) The curves of OS at 5 years will be estimated using the Kaplan-Meier method. The logrank test will be used to test the above hypothesis, the 5-year OS rate difference and its 95% confidence interval (CI) for the comparison between the two groups will be estimated. The minimally invasive surgery will be considered non-inferior to the open surgery if the one-sided 95% upper limit is less than , where = 8%, the predetermined non-inferiority margin.

c) Covariate adjusted analysis:

An analysis of the primary outcome adjusting for the blood loss during operation, operative duration, and postoperative pain score will be performed using Cox proportional hazards regression model. The hazard ratio of 5-year OS and 95% CI will be estimated.

d) Subgroup analysis:

We will stratify by tumour staging, and perform Cox proportional hazards regression model to estimate the hazard ratio and 95% CI of the 5-year OS.

e) Sensitivity analysis:

A sensitivity analysis of the primary outcome will be performed using the PP strategy.

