5.3.3 Secondary outcome analysis

a) The rate of PFS at 5 years:

Cox proportional hazards model will be used to estimate the hazard ratio and 95% CI for the effect of treatment on the 5-year PFS rate.

b) Analysis of continuous outcomes:

The continuous outcomes include operative duration, anesthesia time, blood loss during operation, postoperative pain score and postoperative hospital stay. The outcomes with normal distribution will be summarised using mean and standard deviation (SD), while the outcomes with non-normal distribution will be summarised using median and interquartile. The differences in the outcomes and 95% CIs will be analysed by generalised linear model (GLM) with treatment as fixed effect and with normal distribution and identity link function.

c) Analysis of binary outcomes:

The intraoperative complications, postoperative complications, one-month and one-year postoperative quality of life and sexual life will be treated as binary outcomes, and will

be summarised by number (%) of participants with the event. The differences in the outcomes and 95% CIs will be analysed by GLM with treatment as fixed effect and with binomial distribution and identity link function.

d) Interim analysis

The O'Brien Fleming method will be used to conduct an interim analysis three years after the study. If the study has conducted only once interim analysis, the α level will be set as 0.048 in the final analysis.

4. Safety analysis

Adverse events (AEs) will be summarised using the number of AEs, the number (%) of participants with AEs by groups.

5. All analyses will be performed with a two-sided significance level of 0.05 and conducted using SAS software, version 9.4 (SAS Institute).

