8.1 Definition of adverse events

The Adverse Event (AE) is an adverse medical event that occurs after a patient or a subject in a clinical trial receives a drug, but is not necessarily causally related to the treatment.

Any adverse medical event that occurs in this trial from the time the patient signs the informed consent and receives the treatment until 1 month after the end of the treatment, regardless of whether it is causally related to the surgery performed, is judged as an adverse event, including symptoms, signs, diagnosis, and abnormal laboratory tests.

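### Complications and adverse events are compared only by assigned arm; a prespecified safety analysis by operation begun should be added beside the intention-to-treat comparison

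*Combined protocol and SAP*

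**What the plan says.** Section 5.3.1 sets one general rule: "All analyses will be performed on an intention-to-treat (ITT) basis, except for sensitivity" analysis on a per-protocol basis. Section 5.3.2(e) fixes the scope of that exception: "A sensitivity analysis of the primary outcome will be performed using the PP strategy". No per-protocol, as-treated or operated-population analysis is planned for any other outcome.

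Section 5.3.3(c) says: "The intraoperative complications, postoperative complications, one-month and one-year postoperative quality of life and sexual life will be treated as binary outcomes". They are compared by a binomial model with treatment as the only stated effect, and no population is named. The safety item under the same section reads: "Adverse events (AEs) will be summarised using the number of AEs, the number (%) of participants with AEs by groups". It does not say whether the groups are those assigned or those received, so the reading by assigned arm rests on the general rule in 5.3.1. Section 5.3.4 has a heading that promises a definition of the non-compliant population, but the text beneath it only describes the data monitoring committee. Section 8.1 counts adverse events "from the time the patient signs the informed consent and receives the treatment until 1 month after the end of the treatment", and does not say how this applies to a woman who is not operated on.

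The protocol allows for departures from the assigned operation. Section 3.8 states: "Patients have the right to withdraw from the trial treatment or study at any time without any reason". Section 3.1 states: "If intra-abdominal lesions are found, radical cervical cancer surgery should not be used and should change to palliative treatment". Sections 3.2(g) and 3.3(7) allow radical surgery to be forgone when nodes are positive. Section 3.1 asks for the reason for any conversion from laparoscopic to open surgery. None of these passages says how such women enter the complication or adverse-event tables.

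**The concern.** Comparing complications between the two procedures is a stated secondary research objective. For a harm outcome, shrinking a real difference is not the cautious direction. Two kinds of women cause the shrinkage under a comparison by assigned arm alone:

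- Pre-operative crossovers, whose complications are credited to an operation they did not have.
- Women never operated on, who cannot have an intraoperative complication but may still be counted in the denominator.

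Both are foreseeable. Randomisation comes before surgery, the allocation is then known (Sections 3.13 and 4.2.1), and a woman may leave trial treatment at any time. The background section on surgery versus radiotherapy notes that guidelines recommend chemoradiotherapy for stages IB3 and IIA2, so a non-surgical route exists for this population. At stake is whether the report will contain any table that attributes complications to the operation begun. As the plan stands, it will not.

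**Working it through.** **Figures in the plan.** The documents give no crossover rate, non-operation rate or complication risk, so there is no stated figure for this point to reproduce. The only related number is the sample size in Section 3.12. It reproduces: 495 per group, 495/0.9 = 550, total 1100, next multiple of 6 is 1104, or 552 per group. It is not in question.

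**Formula.** For each arm, with c the share having the other operation from the outset and u the share never operated on:

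risk by assigned arm = (1 - c - u) x risk of own operation + c x risk of other operation + u x 0

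The last term assumes that unoperated women stay in the denominator with no complication.

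**Assumed inputs (none from the documents).**

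| Scenario | Open arm: c, u | Minimally invasive arm: c, u |
|---|---|---|
| 1 | 5%, 3% | 1%, 1% |
| 2 | 10%, 5% | 2%, 2% |
| 3 | 15%, 8% | 3%, 3% |

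**Open surgery more harmful (30% against 20%, true difference 10 points).**

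- Scenario 1: open 0.92 x 30 + 0.05 x 20 = 28.6; minimally invasive 0.98 x 20 + 0.01 x 30 = 19.9; difference 8.7.
- Scenario 2: open 0.85 x 30 + 0.10 x 20 = 27.5; minimally invasive 0.96 x 20 + 0.02 x 30 = 19.8; difference 7.7.
- Scenario 3: open 0.77 x 30 + 0.15 x 20 = 26.1; minimally invasive 0.94 x 20 + 0.03 x 30 = 19.7; difference 6.4.

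**Minimally invasive surgery more harmful (30% against 20%).**

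- Scenario 1: 0.98 x 30 + 0.01 x 20 = 29.6, against 0.92 x 20 + 0.05 x 30 = 19.9; difference 9.7.
- Scenario 2: 0.96 x 30 + 0.02 x 20 = 29.2, against 0.85 x 20 + 0.10 x 30 = 20.0; difference 9.2.
- Scenario 3: 0.94 x 30 + 0.03 x 20 = 28.8, against 0.77 x 20 + 0.15 x 30 = 19.9; difference 8.9.

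So 89-97% of an excess harm of minimally invasive surgery survives, against 64-87% of an excess harm of open surgery. If the assumed rates are exchanged between the arms, the two sets of results exchange as well.

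**Sensitivity to how unoperated women are scored.** If they are treated as missing, each arm is divided by (1 - u). With open surgery more harmful, Scenario 1 gives 28.6/0.97 - 19.9/0.99 = 9.4 points, and Scenario 3 gives 26.1/0.92 - 19.7/0.97 = 8.1 points.

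**Symmetric deviations.** With the same c and u in both arms, the difference by assigned arm is (1 - 2c - u) of the true one. For c and u each between 0 and 10%, that is 70-100%. With 552 per arm, two-sided 0.05 and risks of 10% and 15%, power falls from 71% with no deviations to 45% at c = u = 10%.

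**Why conversions must not be moved.** Suppose 5% of the laparoscopic arm convert with a 50% complication risk and everyone else has 10%. By assigned arm, laparoscopy shows 0.95 x 10 + 0.05 x 50 - 10 = +2.0 points. Counting converted women as open gives an open risk of (55.2 + 13.8)/(552 + 27.6) = 11.9%, so laparoscopy shows -1.9 points. Grouping by the operation completed would reverse the sign.

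**The case against.** The intention-to-treat comparison of complications is a valid randomised comparison of two surgical strategies, and the added comparison is not fully protected by randomisation. That stands. It is a reason to keep the intention-to-treat table and add to it, not to replace it or rank it second.

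The deviations that the protocol spells out, namely conversion and radical surgery abandoned after exploration or positive nodes, all happen after an operation has begun. Grouped by the approach first attempted, those women stay where intention to treat puts them. Only pre-operative crossovers and women never operated on are affected. If they are few, the effect is small. This stands too.

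Three stronger readings are tempting but are not supported:

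- A reader might infer that refusal will be higher in the open arm, because Section 2.4 says of most leading hospitals in China that "laparoscopic radical cervical cancer treatment accounts for more than 90% of the cases". That describes hospital practice, in a paragraph on early-stage disease, not patients' preferences at stages IB3 and IIA2. The same section says guidelines now recommend open surgery and no longer recommend laparoscopy. Refusal could be higher in either arm.
- A reader might infer a spurious difference where none exists. With a 30% risk in both arms, the three scenarios show the minimally invasive arm 0.6, 0.9 and 1.5 points worse. This requires unoperated women to be scored as event-free, which the plan does not state. If they are treated as missing, the artefact is zero.
- A reader might infer that unoperated women necessarily have no adverse events. The treatment in Section 8.1 is not defined for them, and a woman given radiotherapy instead may have events. The denominator point is firmest for surgical complications.

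Finally, Section 5.3.1 calls itself an overview and promises a detailed analysis plan, which might define a safety set. The current rule nevertheless covers all analyses, and should not be left for a later document to contradict.

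**Conclusion.** The point holds as a gap in the safety analysis. Followed as written, the plan yields no complication or adverse-event comparison by operation begun, and the comparison by assigned arm tends to dilute a difference in surgical harm. The size and direction cannot be determined from the documents. Under the assumed rates, a true 10-point difference becomes 8.7 to 6.4 points if open surgery is the more harmful and 9.7 to 8.9 if minimally invasive surgery is. With few deviations the loss is minor. For adverse events, the conclusion rests on applying the general rule in 5.3.1 to an undefined grouping term. Nothing here makes the intention-to-treat comparison wrong or touches the primary analysis. It is a cheap and worthwhile addition.

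**What to change.** Keep the intention-to-treat comparison. In Sections 5.3.1 and 5.3.3, prespecify an additional safety analysis of intraoperative complications, postoperative complications and adverse events in all women whose operation was begun, grouped by the approach first attempted. Women converted to open surgery stay in the minimally invasive group. Report by arm the numbers crossed over before surgery, converted, and never operated on. Use Section 5.3.4 to say how unoperated women are scored in the intention-to-treat complication table.

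The cost is a few sentences and one extra set of tables. No new data should be needed, since Section 3.7.2 already records details of the procedure and Section 3.1 the reasons for conversion. The downside is that the added comparison is not fully protected by randomisation, so it should be presented beside the intention-to-treat table and fixed before results by arm are seen.
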